07/02/2020	07/23/2020	3.5	Make ICF and SmartForm consistent	[name]
09/06/2020	09/13/2020	3.6	Recruit through Crofoot appointment confirmation email/texts	[name]
10/28/2020	11/27/2020	3.8	Change time between Visit 1 and 2 to six months	[name]
12/17/2020	02/08/2021	3.9	Update visit 2 procedures, recruitment section to include referral program.	[name]

			Move participant's anal self-exam (ASE)/ anal companion exam (ACE) at Visit 2 from in-clinic to at-home due to COVID-19.	
08/12/2021	02/14/2022	4.0	
Add clinic site in Houston
 
[name] transitions to MD Anderson
 
Thomas Street Health Center added as clinic site in Houston under purview of MD Anderson,
 
Remove some clinicians' names and replace with text that does not need to be altered when clinicians change.
	[name]
03/07/2022	05/15/2022	4.1	
Send participants notice of ANCHOR Study results
 
Revise Protocol Change History table to add Date Approved column and modify Revisions column text to better identify amendment
 
Remove medical records review activity.
	[name]
05/25/2022	05/15/2022	4.2	Increased number to take eligibility survey to 2500.	[name]
11/02/2022	11/12/2022	4.3	This version accompanies Amendment 26160 which increases the number in the PROSmartForm of those who will take the eligibility survey to 3500 and increases the number to consent to 1050. Number to screen and number to consent do not appear in this protocol; thus no change is made to the protocol.	[name]
3/10/2023	05/04/2023	4.4	Sending new survey to PAC Palp participants	[name]
10/16/2023	12/20/2023	4.5	Add MUSC as getting a de-identified dataset	[name]

## LIST OF ABBREVIATIONS

ACE	Anal Companion Exam
ASE	Anal Self-Exam
CAB	Community Advisory Board
CASI	Computer-Assisted Self-Interview
CE	Cost-effectiveness
DARE	Digital Anal Rectal Exam
HRA	High-Resolution Anoscopy
HPV	Human Papillomavirus
LGBT	Lesbian, Gay, Bisexual, and Transgender
MCW	Medical College of Wisconsin
MSM	Men Who Have Sex with Men
PAC	Prevent Anal Cancer
TSM	Transgender Persons Who Have Sex with Men

## STUDY SYNOPSIS

This is a clinical trial of the sensitivity and specificity of anal self-exams and anal companion exams to detect early invasive anal cancer among Chicago and Houston HIV-positive and HIV-negative men who have sex with men (MSM) and transgender persons who have sex with men (TSM).

## MULTI-CENTER STUDY

Medical College of Wisconsin (MCW) is the lead agency in the study. MCW will coordinate activities among study sites and receive all study data. Data will be coded, collected and shared with co-Investigators using REDCap (Vanderbilt University).

- 1) The University of Chicago (UChicago) staff/faculty will have participant contact during recruitment and when participants come for clinic visits at UChicago.
- 2) Staff of the Crofoot Clinic in Houston will have participant contact during recruitment and when participants come for clinic visits at Crofoot Clinic.
- 3) Staff/faculty of The University of Texas Health Science Center at Houston School of Public Health (UTHealth) will have participant contact during recruitment, when participants come for clinic visits at Crofoot Clinic and when analyzing qualitative data.
- 4) Staff/faculty of MD Anderson will have participant contact during recruitment and when participants come for clinic visits at Crofoot Clinic or Thomas Street Health Center and when faculty view study procedures at the Crofoot Clinic for quality control purposes.
- 5) MCW staff/faculty will have participant contact during recruitment and when participants come for clinic visits at UChicago, the Crofoot Clinic, and Thomas Street Health Center.

All study data will be collected and sent to MCW which will aggregate and analyze the data to complete Aims 1 and 2. UTHealth will analyze these same data for completion of Aim 3.

## BACKGROUND

Anal cancer is a common cancer among gay, bisexual and other men having sex with men (MSM). Its annual incidence is approximately 50-fold and 5-fold higher among HIV-positive MSM and HIV-negative MSM, respectively, compared to the rest of the general population. Like cervical cancer, it is primarily caused by human papillomaviruses (HPV). Unlike cervical cancer, there is no efficacious treatment for anal precancers as there is for cervical precancers. To date, randomized clinical trials have failed to find an efficacious treatment although other trials continue; thus, professional societies recommend an annual Digital Anal Rectal Exam (DARE) for detection of anal abnormalities, including small tumors, among all MSM. But DARE is underutilized, e.g., most persons, regardless of HIV do not receive an annual DARE and most HIV physicians do not perform the exam. Therefore, alternative methods for early detection are needed because early detection of small tumors is associated with >85% 5-year survival.

To increase detection of anal canal tumors, our NCI-funded phase II pilot study in Houston, Texas determined it was feasible to teach MSM to palpate their own, or their companion's, anal canal. Acceptability was 94% among 148 individuals doing the exam on themselves (anal self-exam, ASE) and 92% among 52 couples doing the exam on their companion (anal companion

exam, ACE). There was 93% concordance between the clinician's gold-standard DARE and the participants' ASE or ACE for any anal canal abnormality.

## **STUDY PURPOSE**

The long-term goal of the Prevent Anal Cancer (PAC) Palpation Study is to decrease morbidity and mortality from anal cancer by increasing detection of anal canal tumors through self- or partner-palpation of the anal canal.

Having established feasibility among MSM to detect an anal abnormality, next steps are to derive robust estimates of accuracy for both ASE and ACE (e.g., increased sample size in the current study), assess if another clinic can replicate the R21 finding (i.e., UChicago), and assess cost-effectiveness of these exams. In this protocol, "accuracy" is a general term for test operating performance and predictive value. It includes our outcomes of concordance, sensitivity, specificity, positive predictive value, and negative predictive value.

Our central hypothesis is that both ASE and ACE at Visit 1 will have  $\geq 70\%$  sensitivity and  $\geq 90\%$  specificity compared to the clinician DARE gold standard; thus, we believe this study will demonstrate that MSM can recognize when disease is present. We will test the hypothesis with three specific aims:

## **AIMS**

### **Aim 1: Estimate ASE and ACE sensitivity and specificity.**

Hypothesis: ASE and ACE sensitivity will be  $\geq 70\%$  and  $\geq 78\%$ , respectively, at Visit 1; specificity will be  $\geq 90\%$  on both exams, and there will be no difference in ASE sensitivity between Houston and Chicago clinics.

Objective: Our objective in this aim is to compare the men's ASE or ACE result with the clinician gold-standard DARE to determine sensitivity and specificity for each exam at two time points.

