After the post-exam CASI, participants will remain in the exam room (couples will be reunited) and receive DARE results. If the screening result is a true negative (either for an individual, or, for couples, both partners), the study coordinator will provide the results, e.g., “You reported that your anus felt and looked normal and that’s what the clinician said too. So now you know what your anus is like when it’s completely normal. If something changes, you’ll be better able to notice there’s a difference.” If the result is a true positive, false positive or false negative, then the clinician will provide the result.

If there is a finding of an abnormality on DARE, then standard clinical practices will be followed. If needed, clinicians will treat limited external disease, triage other disease, and ask the participant to call if there are any concerns in the following week. If the result is a false positive or false negative, the clinician will request to immediately perform a second DARE for adjudication of the discordant result. All participants with referrals due to abnormal DAREs will be followed to assess care-seeking behavior and outcome.

An exploratory aim of this study is to collect qualitative data at Visit 1 from all persons with a false-positive, false-negative, or true-positive result and a 5% random sample of true-negatives (~65 persons in each city based on pilot data, or ~1 per clinic week over 2 years). Each will be invited to participate in an individual interview of up to 15-minutes conducted by a member of the project team at each clinical site. Interviews will explore anxiety among persons with discordant results and any needed support. Faculty will train staff to use a semi-structured guide for interviews.

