## STATISTICAL ANALYSIS

### Aim 1

The central hypothesis is that both ASE and ACE at Visit 1 will have  $\geq 70\%$  sensitivity and  $\geq 90\%$  specificity using the clinician DARE as the gold standard. We will test our central hypotheses at Visit 1 by comparing ASE and ACE sensitivity and specificity to random guessing (i.e., sensitivity and specificity=50%) using a one-sample test for proportion. We will then conduct a test of equivalence using two, one-sided likelihood score tests to compare ASE sensitivity in Houston vs Chicago clinics to determine if the ASE performance is equivalent in each city; thus, we will assess the homogeneity of Houston and Chicago sensitivity before combining results. We focus on sensitivity since this factor performed worse than specificity in the pilot study and had wide confidence limits. Sensitivity will also be stratified by other factors, for example location (anal canal vs perianal) and co-morbidities, to determine the effect on sensitivity. Tests will be two-sided with a 0.05 alpha. We will estimate percent agreement, positive predictive value, negative predictive value and perform receiver operating characteristic (ROC) curve analysis for a binary outcome.

To test our central hypothesis, our pilot data indicate 1) 11% of persons will have condyloma, hemorrhoids, skin tags, scars, or malignant tumors at Visit 1 at the anal canal or perianal region, and 2) a sensitivity of  $\geq 70\%$  on ASE and 78% on ACE and specificity  $\geq 90\%$  for both at Visit 1. Given a null value for sensitivity and specificity of 50% (since we seek to rule out accuracy due only to chance), our power to detect sensitivity  $\geq 70\%$  among 600 individuals is 0.90 and 0.81 among 200 couples. Power to detect specificity  $\geq 90\%$  among both individuals and couples is  $>0.90$ . For multiple comparisons we will use the False Discovery Rate. Using a test of equivalence, our hypothesis of no difference in ASE sensitivity between Houston and Chicago assumes that a difference of less than 0.15 constitutes equivalent sensitivity given that a smaller difference may have little practical relevance for adjusting the protocol in either city. Under this definition of equivalence, we have at least 0.87 power to detect a lack of equivalence in sensitivity between the cities if the actual observed difference ranges from 0 to 0.05. Power was assessed with PASS13.

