For the Aim 2 hypothesis, that practice will be associated with concordance in all persons at Visit 2, sample size will be adjusted downward by dropouts and non-resolving abnormalities from Visit 1. We expect 11% of persons ( $n=88$ ) to have an abnormality at Visit 1 (based on pilot data) with most of these being hemorrhoids and condyloma. We conservatively expect 50% of hemorrhoids and condyloma to resolve in 9 months; thus, there will be a minimum of 44 non-resolving events from Visit 1 and another 10% of persons will dropout ( $800-44=756$ ;  $756-76=680$ ). We have 80% power to detect an odds ratio of at least 1.55 or larger if concordance is 85% and  $n=680$ .

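### Visit 2 sensitivity is at risk of upward bias from abnormalities already disclosed at Visit 1, and the plan does not say how these are handled

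*Combined protocol and SAP*

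**What the plan says.** The Aim 1 objective is to compare participant and clinician results "to determine sensitivity and specificity for each exam at two time points". The formal test is confined to the first visit: "We will test our central hypotheses at Visit 1 by comparing ASE and ACE sensitivity and specificity to random guessing" (Statistical Analysis, Aim 1).

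At Visit 1 the participant does the self- or companion exam before hearing the clinician's finding. Afterwards, "participants will remain in the exam room (couples will be reunited) and receive DARE results". For anyone with an abnormality, found or missed, disclosure comes from the clinician: "If the result is a true positive, false positive or false negative, then the clinician will provide the result" (Visit 1 Detail).

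On prevalence, pilot data suggest that "11% of persons will have condyloma, hemorrhoids, skin tags, scars, or malignant tumors at Visit 1" (Statistical Analysis, Aim 1). On persistence, the Aim 2 sample-size text says "We conservatively expect 50% of hemorrhoids and condyloma to resolve in 9 months" and concludes that "there will be a minimum of 44 non-resolving events from Visit 1 and another 10% of persons will dropout". It then removes both groups from the Aim 2 count.

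Under Preparation for Visit 2, everyone is asked back whatever the earlier result. Only people with an uncleared contraindication skip the second exam. It is done at home in the day before the clinic visit and reported by text as normal or abnormal.

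The Aim 1 analysis text gives no rule for abnormalities already recorded at Visit 1. Its examples of stratifying factors are location and co-morbidities. The Aim 2 analysis text does not repeat the exclusion used in the Aim 2 sample size.

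**The concern.** At Visit 1 an abnormal report means that the participant found something. At Visit 2, a person told six months earlier of a lesion that has not resolved may report abnormal from memory. The single normal/abnormal text cannot separate the two. Some of these people missed the lesion the first time and know of it only because the clinician told them.

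The study's stated goal is earlier detection of tumors, so the relevant quantity is sensitivity for lesions that the person does not yet know about. If the pooled Visit 2 sensitivity exceeded the Visit 1 figure, it could be taken as retained or improved skill when part of it is recall. The Aim 3 text says that study data will supply screening test characteristics without saying which visit's estimate is used, so the pooled figure is not ruled out as a model input.

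Specificity has a related problem. A person whose disclosed lesion has resolved may still report abnormal from memory, which would count as a false positive.

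**Working it through.** **1. The plan's own counts reproduce.**
- Abnormal at Visit 1: 800 × 0.11 = 88.
- Not resolving: 88 × 0.50 = 44.
- Aim 2 sample size: 800 − 44 = 756; 10% dropout is 75.6, rounded to 76; 756 − 76 = 680.
- If the 10% dropout also applies to the 44, 44 × 0.90 = 39.6, so about 40 return.

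The resolution rate is stated over 9 months, but Visit 2 is at 6 months. Persistence at Visit 2 could be higher than 44, and the two intervals need reconciling.

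**2. Lesions known only through disclosure.** At the hypothesised sensitivity of 70%, 44 × 0.30 = 13.2. So about 13 of the 44 persistent abnormalities would have been missed by the participant at Visit 1 and then disclosed.

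**3. Effect on the pooled Visit 2 estimate.** Let
- *s* = sensitivity for abnormalities not previously disclosed, set at 0.70 (the plan's ASE hypothesis);
- *k* = probability that a persistent, known abnormality is reported (not in the documents; assumed 0.70 to 1.00);
- *m* = number of new abnormalities at Visit 2 (not in the documents; assumed 10 to 66);
- *f* = 44 / (44 + *m*), the share of Visit 2 DARE-positives that are already known.

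Pooled sensitivity = *f*·*k* + (1 − *f*)·*s*, so the bias is *f*·(*k* − *s*).

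| New (*m*) | *f* | *k* = 0.70 | *k* = 0.80 | *k* = 0.90 | *k* = 1.00 |
|---|---|---|---|---|---|
| 10 | 0.815 | 0.700 | 0.781 | 0.863 | 0.944 |
| 22 | 0.667 | 0.700 | 0.767 | 0.833 | 0.900 |
| 44 | 0.500 | 0.700 | 0.750 | 0.800 | 0.850 |
| 66 | 0.400 | 0.700 | 0.740 | 0.780 | 0.820 |

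Example: *m* = 22, *k* = 0.90 gives 0.667 × 0.90 + 0.333 × 0.70 = 0.833, or 13 points above 0.70.

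Across the table the bias is 0 at *k* = 0.70, 4 to 16 points for *k* = 0.80 to 0.90, and 24 points at the extreme (*k* = 1.00, *m* = 10). Using 40 persistent abnormalities instead of 44 lowers these figures by less than 1 point.

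**4. Precision if only undisclosed abnormalities are used.** Normal-approximation 95% half-width at 0.70: 1.96 × √(0.70 × 0.30 / *m*).
- *m* = 10: 0.28
- *m* = 22: 0.19
- *m* = 44: 0.14

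The approximation is rough at *m* = 10. Estimates for ASE and ACE separately would each rest on part of these counts.

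**The case against.** The strongest reply is that the plan commits to nothing wrong here. It sets no Visit 2 denominator for Aim 1. If the Aim 2 exclusion is meant to apply throughout, the bias largely disappears. That is fair: this is an unstated rule, not an incorrect one. But nothing in the text extends the exclusion to Aim 1, and the Aim 2 analysis text does not carry it either.

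A reader might infer that Visit 2 sensitivity will certainly be inflated, and by a definite amount. The documents do not support that, because they give neither the reporting rate for known lesions nor the number of new ones. Opposing pressures exist: someone told that a scar or skin tag is benign may record normal, and the Visit 2 exam is done at home without repeat training.

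A reader might also infer that most Visit 2 abnormalities will be known ones. That holds only if fewer than 44 new ones appear (about 40 after dropout).

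The consequences can be overstated too. The central hypothesis and its power concern Visit 1, before disclosure. No comparison of sensitivity between visits is planned, and Aim 3 does not explicitly name a Visit 2 input. Both randomised arms receive their Visit 1 results. All of this stands and limits the point to a secondary, untested estimate. It does not make the pooled estimate interpretable.

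Finally, with one normal/abnormal report, a person with both an old and a new lesion cannot be credited with finding the new one. That is correct, so stratification must be by person, not by lesion.

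**Conclusion.** The point holds as a risk of upward bias in one secondary Aim 1 estimate, combined with a missing handling rule. The mechanism rests on the documents: disclosure to everyone, at least 44 of 88 abnormalities expected to persist, and nearly all of those people repeating the exam with a single binary report.

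The size does not come from the documents. With *s* = 0.70, 44 persistent and 10 to 66 new abnormalities, it runs from 0 to 24 points, with 4 to 16 points if known abnormalities are reported at 80 to 90%. Benign findings recorded as normal, or the home exam without retraining, could push the estimate the other way.

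The Visit 1 hypothesis tests and their power are not affected. This is a cheap improvement to the analysis plan, not a flaw in the main result.

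**What to change.** - In the Aim 1 analysis text, report Visit 2 sensitivity and specificity at person level by Visit 1 DARE status (normal or abnormal).
- Base any statement about retained ability to find unknown lesions on participants with a normal Visit 1 DARE.
- Do not use the pooled Visit 2 sensitivity as an Aim 3 input. Use the pre-disclosure Visit 1 estimate, or the Visit 2 estimate in participants with a normal Visit 1 DARE.
- Carry the exclusion of non-resolving abnormalities from the Aim 2 sample size into the Aim 1 Visit 2 and Aim 2 analysis text, or state that it does not apply.
- Reconcile the 9-month resolution assumption with the 6-month visit interval.

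The cost is one stratified table and a few sentences. The DARE result is already recorded on the same form at both visits, so no new data are needed. The downside is imprecision: few new abnormalities are likely, and the half-widths of 0.14 to 0.28 above should be expected. A wide interval around the relevant quantity is still more useful than a narrower one around a mixture.

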### **Aim 2: Determine independent factors associated with ASE and ACE concordance.**

Hypothesis: We postulate that practicing the ASE or ACE between visits will be associated with concordance between the ASE/ACE and DARE at Visit 2.

Objective: Using regression analysis, determine factors associated with ASE and ACE concordance.

### **Aim 3: Determine the impact of ASE, ACE, and DARE on survival and quality of life, and evaluate the cost-effectiveness of these strategies among HIV-positive and HIV-negative MSM.**

**Hypothesis:** We hypothesize that initiating training to perform annual ASE or ACE as early as age 30 will lead to cost-effective use of health care resources and will have long-term health benefits relative to no ASE or ACE.

**Objective:** Complete an economic and survival analysis of ASE, ACE, and DARE using mathematical modeling.

**Exploratory aim:** Collect qualitative data at Visit 1 from all persons with a false-positive, false-negative, or true-positive result and a 5% random sample of true-negatives to explore participants' feelings about the ASE/ACE including anxiety among persons with discordant results and any needed support.

## **OUTCOMES**

Our expected outcomes for aims 1 and 2 are sensitivity, specificity and identification of clinical and behavioral factors associated with concordance. The outcomes of aim 3 will be the computation of incremental cost-effectiveness ratios and net monetary benefits to assess the economic viability of ASE, ACE, and DARE. Data on these outcomes are necessary to provide options for anal cancer screening given underutilization of DARE, no proven precancer treatment efficacy, poor infrastructure for a Pap cytology-based precancer screening protocol, and stigma-related barriers that delay clinic attendance for anogenital examinations. Data from the proposed study could propel the development of a patient-centered intervention for rapid dissemination to a population with extremely high anal cancer incidence and no currently proven screening options.

## **SAMPLE SIZE**

800 participants completing Visit 1: 400 in Chicago and 400 in Houston

## **POPULATION**

We will recruit MSM and TSM, aged 25 years and over, who acknowledge sex with men in the last five years or have a minority sexual orientation, have no unresolved health care provider's diagnosis of anal condyloma, hemorrhoids or anal cancer, speak either English or Spanish, have not had a DARE in the prior 3 months, have no plans to move in the following 6 months, and have access to medical care for any needed referral and treatment that may be discovered during the study.

## **DURATION OF PARTICIPANT ACTIVITIES**

6 months

Study Timeline																				
	2018		2019				2020				2021				2022				2023	
Quarter	q3	q4	q1	q2	q3	q4	q1	q2	q3	q4	q1	q2	q3	q4	q1	q2	q3	q4	q1	q2
Human subjects approvals																				
Initiate/meet with CABs																				
Complete protocol/build CE models																				
Pilot full protocol & adjust																				
Train clinicians and observe																				
Visit 1 clinics																				
Interim ASE/ACE practice reminders																				
Visit 2 clinics																				
Data cleaning & analyses (Aims 1, 2)																				
CE analyses (Aim 3)																				
Submit abstracts & manuscripts																				

## **PARTICIPANT ENROLLMENT**

Participants in each city must meet all stated eligibility criteria.

